10.0 Statistical Analysis Plan

The calculation of the average daily numeric pain scores, the average number of opioid dosage increases, and average daily opioid amounts (mg of morphine equivalents) will be evaluated. In addition, the secondary measures of, oxygen saturation, heart rate and body weight, findings from the Edmonton numeric assessment scale: nausea/vomiting, appetite, depression, anxiety and overall well-being will be examined.

There will be a database for tracking all primary and secondary data.

Sample size determination

See sample-size calculation and justification under "Study Population" (section 6.0).

Missing, unused, and spurious data

Missing, unused, and spurious data will be documented ongoing and noted in the final study results.

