3.0 Objectives

Primary

1. Improve pain management as identified by decreased overall numeric pain scores
2. Reduce opioid dosage increases
3. Reduce overall opioid utilization

Secondary

Evaluate changes in patient weight, appetite, nausea and vomiting, O2 saturation, feelings of well-being, anxiety, and depression.

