4.0 Study Design and Methodology

Design

This will be an open-label study. Patients will choose to participate in a Marijuana adjuvant treatment group, receiving marijuana in combination with standard opioid therapy.

The goal is to enroll at least 66 Hospice patients in the study.
Methodology

Patients will be notified of the study's existence through communication with the study's investigation team at time of admission. Patients will be screened for study eligibility—see section 6.0 for study eligibility factors—and if the patient is both eligible and interested in participating, the sub-investigator will discuss and review the informed consent form with the patient and obtain their signature; the patient will then have a consultation with a prescribing physician; and, if the physician has determined that medical marijuana is a viable option for that patient, registration with the Connecticut Medical Marijuana program will begin. For patients who have already been prescribed both marijuana and opioid medication upon admission to Hospice, signing the consent form will complete study enrollment.

Patients' initial opioid dose, dosing schedule and numeric pain score will be recorded. For the duration of the study (at least five days) changes in opioid doses and numeric pain scores will be tracked daily.

Marijuana will be administered to the patient via oral route three times daily for at least five days. Patients will receive CBD:THC product provided by NIDA.

On admission to the study, a modified Edmonton Symptom assessment scale to quantify baseline appetite, depression, nausea, vomiting, overall well-being, and anxiety.

Data Tracking: Primary objective tracking will include average numeric pain scores and number of opioid dosage increases and average daily opioid amount (mg equivalents of morphine).

Secondary objectives include Weight, Appetite, N/V, O2 Saturation, Self-reported data points from the modified Edmonton Assessment Scale.

Data Tracking Intervals: Primary objective tracking of pain will be daily every 4 hours (twice per shift). Secondary objective tracking as follows: Weight daily, Appetite every 8 hours (every shift), N/V, O2 saturation as reported by clinician documentation, Edmonton scale results three times weekly.

Analysis

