Following the data collection phase, investigators will calculate average numeric pain scores, average number of increases in opioid dosage and average daily opioid amount (mg equivalents of morphine). Analysis will examine whether the addition of CBD/THC with opioid therapy had

a stabilizing effect or improvement in pain management (lower average numeric pain scores, few dosage increases, lower opioid doses and subsequently less opioid therapy needed)

Additionally calculations will include results of changes in weight, calculation of average changes in O2 saturation, and average changes in Edmonton-Scale scores for secondary data collection points.

Patient Selection to Ensure Validity

The study will enroll patients with a primary diagnosis (Table 1) of cancer and non-cancer with associated pain considered to have a terminal illness requiring end of life care, utilizing routine or as needed opioid therapy for pain.

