5.0 Study Population

Adult (≥18 years of age), non-pregnant, alert and oriented hospice inpatients. Subjects must take opioids for pain management either routinely scheduled or on an as needed basis to qualify.

Inclusion / Exclusion Criteria

Included: alert adults (age 18+) requiring opioids for pain management (routine or as needed) with a cancer diagnosis or non-cancer diagnosis as their terminal illness as defined in Table 1 .

Excluded: pregnant women, children (patients < 18 years of age), minimally or unresponsive patients unable to take oral medications, and agitated combative patients.

Sample Size

66 patients is the target.

The average length of stay at The Connecticut Hospice, Inc. is twelve days. At the end of each nine day cycle (i.e. the time by which the average patient has three days to live), we can expect roughly thirty-five out of thirty-nine inpatients to take opioid medication(s) to manage pain.

Since the study will happen over about 180 days, this means the population size for the length of the study should be about 700 patients.

Therefore, assuming a 95% confidence interval, a 5% error margin, and a statistical significance level of .05, we have calculated a target sample size of 66 patients.

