6.0 Study Agent and Intervention Description

Options

Capsules: 40 mg/1 .5 mg or 80 mg/3 mg CBD:THC per capsule (Gelatin capsules: Apothecon).

Interventions

All patients and marijuana naive (no marijuana use within the last 30 days) will receive 40/1.5 mg CBD:THC three times daily. Marijuana tolerant patients (Marijuana use currently or within the last 30 days) will receive 80 mg/3 mg CBD: THC three times daily.

Patients who experience three scheduled opioid dosage increases while receiving the 40 mg/1 .5 mg regimen will have an increase to the 80 mg/3 mg dosage three times daily for the remainder of the study.

Security/Records

All study drugs will be secured abiding by federal and state regulations for storage of Scheduled substances.

Running inventory will be maintained for all study product. The pharmacy staff will record receipt and dispensing of study product, and maintain adequate supply and availability for the study population in accordance with all federal narcotic regulations.

Storage of Scheduled study product will be accessible to pharmacy personnel and clinical staff caring for the patient, in accordance with the hospital's policies and procedures and in accordance with both state and federal storage requirements.

7.0 Study Schedule:

Patients must have, at minimum, a 3-day life expectancy

SCREENING

ENROLLMENT

DOSING -5 Ongoing Assessment of Patient Progress and Safety

DATA COLLECTION

DATA ANALYSIS

Adverse/Serious Adverse Events: dysphoria, extreme anxiety/panic attack, paranoia, psychosis, ataxia, impaired motor coordination, any condition that would typically not be associated with the patients admitting diagnosis or normal course of illness.

Adverse reactions will be immediately documented on the Connecticut Hospice Adverse Drug Reaction Form and evaluated by the PI and clinical investigation team. The research team will

determine whether changes to the study protocol, including discontinuation of the study, are warranted.

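### The primary measure of opioid dosage increases has no time denominator, so its average partly reflects how long patients were observed

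*Combined protocol and SAP*

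**What the plan says.** Section 3.0 lists "Reduce opioid dosage increases" as the second primary objective. Three places describe how it is measured:

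- The data-tracking paragraph of section 4.0 names the number of increases as a tracked item and gives no time unit.
- The analysis paragraph of section 4.0 plans the "average number of increases in opioid dosage and average daily opioid amount (mg equivalents of morphine").
- Section 10.0 will evaluate "the average daily numeric pain scores, the average number of opioid dosage increases, and average daily opioid amounts (mg of morphine equivalents").

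On follow-up, section 4.0 states: "For the duration of the study (at least five days) changes in opioid doses and numeric pain scores will be tracked daily". No maximum is given. Section 5.0 adds that "The average length of stay at The Connecticut Hospice, Inc. is twelve days", and section 7.0 requires a life expectancy of no less than three days.

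On interpretation, section 4.0 describes stabilization or improvement as "lower average numeric pain scores, few dosage increases, lower opioid doses and subsequently less opioid therapy needed". The design is open-label with a single treatment group.

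**The concern.** In the section 10.0 list, the measures on either side of the count are daily averages, so they do not grow simply because a patient stays longer. The count does. Each further day on study is another day on which a dose can be raised.

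Follow-up will vary in this population, because patients are dying inpatients with a floor on follow-up but no ceiling. Two cohorts with the same daily rate of increases could then report different averages only because one was observed longer. The plan takes few increases as a favourable sign and has no concurrent group with the same follow-up pattern. The absolute average is therefore what will be read, and a reader could not tell how much of it is pain control and how much is length of observation.

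**Working it through.** **Plan's own figure.** The plan states no expected count, rate or target for this measure, so there is nothing to reproduce. Its one computed figure, the target of 66 patients, does not use the count.

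**Inputs.**
- 5 days: the minimum follow-up in section 4.0.
- 12 days: the institution's average stay in section 5.0, used here only as a plausible longer follow-up.
- Daily rate of increases: not given in the documents. I assume 0.1 to 0.5 per day, constant over time.

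**Step 1: count as planned.** Expected count = rate × days observed.

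| Assumed rate per day | 5 days | 12 days | Ratio |
|---|---|---|---|
| 0.1 | 0.5 | 1.2 | 2.4 |
| 0.2 | 1.0 | 2.4 | 2.4 |
| 0.5 | 2.5 | 6.0 | 2.4 |

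The ratio is 12/5 = 2.4 at any constant rate, because the rate cancels.

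**Step 2: count per patient-day.** At 0.2 per day, the 5-day patient gives 1.0/5 = 0.20 and the 12-day patient gives 2.4/12 = 0.20. Pooled, (1.0 + 2.4)/(5 + 12) = 3.4/17 = 0.20. Length of follow-up no longer moves the result.

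**Step 3: common window.** Over days 1 to 5, both patients have an expected count of 0.2 × 5 = 1.0.

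**Step 4: if the rate is not constant.** Suppose the 12-day patient has 0.2 increases per day, a count of 2.4. The 5-day patient reaches the same count at 2.4/5 = 0.48 per day, which is 2.4 times the rate. If increases cluster near death strongly enough to exceed that, the shorter follow-up shows the higher count. The dependence on follow-up remains, but its direction is not fixed.

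**Step 5: weighting in the pooled rate.** Of the 17 patient-days in step 2, the longer-stay patient supplies 12/17 = 71% and the shorter-stay patient 5/17 = 29%. The pooled rate therefore leans towards patients who stay longer.

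**The case against.** **The study is an exploratory pilot with descriptive averages, and doses are tracked daily, so a rate can be derived later.** This is true, and it is why the repair is cheap. But the rate is not planned, and choosing a denominator after seeing open-label data is weaker than stating it beforehand.

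**The lengths used are not study follow-up.** This stands. Twelve days is the institution's average stay, and section 5.0 uses it in sizing the population. For patients not already prescribed marijuana, consent, a physician consultation and state registration come before dosing, so days on study would usually be fewer. The schedule in section 7.0 also has a damaged line that may be what is left of a five-day dosing window. It does not override the open-ended minimum in section 4.0, but it is a reason for some caution about how far follow-up extends.

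**No text says the average is per patient.** Also true. What the documents show is an unstated denominator. A count per patient is the natural reading, and the calculation rests on it.

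**A reader might infer that a shorter stay will look like benefit.** The documents do not support that. They give no comparator, historical rate or threshold for how few increases is few, and the rate may rise near death.

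**A reader might also infer that the count is unusable because an increase is not defined.** Section 5.0 does admit patients on as-needed opioids: "Subjects must take opioids for pain management either routinely scheduled or on an as needed basis to qualify". However, the ordinary meaning of a dosage increase for an inpatient is a change in the ordered dose, and as-needed use should already show in the daily morphine-equivalent amount. The word scheduled in section 6.0 ("Patients who experience three scheduled opioid dosage increases while receiving the 40 mg/1 .5 mg regimen will have an increase") belongs to the rule for raising the study drug and does not bear on the time base.

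**Conclusion.** The point holds for the time base. A primary measure is summarized without a denominator while follow-up is open-ended, so its average mixes the rate of increases with the days observed. The size is a factor of 2.4 between 12 and 5 days. That figure assumes a constant daily rate, a count taken per patient, and two illustrative lengths of follow-up. The effect on the trial average cannot be sized, because the distribution of follow-up is not given. The direction of any bias is not shown. A daily rate would not supply the missing comparison, so even the corrected measure cannot by itself establish benefit.

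**What to change.** Use the same wording in the data-tracking and analysis paragraphs of section 4.0 and in section 10.0:

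1. Report opioid dosage increases as total increases divided by total patient-days on study, with the range of days followed.
2. Beside it, show the count over days 1 to 5, with the number of patients observed for all five days. This window matches the protocol's own minimum and guards against a rate that changes near death. Patients who die or leave before day 5 still contribute less, so that number needs to be visible.

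Optionally, add a clause saying that an increase means a change in the ordered dose.

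The cost is one extra summary. No new data are needed, because the initial dose and schedule are recorded and dose changes are tracked daily. The drawback is that the pooled rate gives more weight to long-stay patients, which the days 1 to 5 count helps the reader to judge.

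### With no rule for death, discharge or loss of self-report, the primary averages can shift because the patients measured change, and raw counts of opioid increases are cut short

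*Combined protocol and SAP*

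**What the plan says.** Section 10.0 (Statistical Analysis Plan) lists what will be evaluated for the primary objectives: "The calculation of the average daily numeric pain scores, the average number of opioid dosage increases, and average daily opioid amounts". The Analysis part of section 4.0 names the same three summaries and treats lower pain scores, few increases and lower doses as evidence of benefit. The whole rule for incomplete data, in section 10.0, is "Missing, unused, and spurious data will be documented ongoing and noted in the final study results".

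Follow-up and entry are described in three places:

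- Section 4.0: capsules are given "three times daily for at least five days", and "For the duration of the study (at least five days) changes in opioid doses and numeric pain scores will be tracked daily". Initial opioid dose and pain score are recorded.
- Section 7.0 (Study Schedule): "Patients must have, at minimum, a 3-day life expectancy".
- Section 5.0 (Sample Size): "The average length of stay at The Connecticut Hospice, Inc. is twelve days". The next sentence there treats this stay as time to death, putting the average patient three days from death after nine days.

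Section 5.0 excludes "minimally or unresponsive patients unable to take oral medications" at entry. Nothing says what happens to the data of a patient who becomes unresponsive or unable to swallow later. No section gives an analysis set, a denominator, a model, a sensitivity analysis or an allowance for early loss. There is one open-label group and no comparator.

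**The concern.** A patient may enter with a shorter expected survival than the minimum tracking period, so truncated records are part of the design. Two consequences follow if the summaries are computed as named.

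First, an average for a later day rests on fewer and different patients than the baseline average. It can rise or fall with no change in any patient. With no control arm, nothing in the study separates that shift from a drug effect, and section 4.0 would read a fall as stabilised or improved pain management.

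Second, a count of opioid increases cannot grow after a patient leaves. A short stay yields a small count, and few increases is one of the plan's marks of success.

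**Working it through.** **The plan's own figures.** The documents give no expected rate of early loss, so there is none to reproduce. The target of 66 reproduces as a precision calculation for one proportion if that proportion is 0.05 or 0.95, which the plan does not state: n0 = 1.96² × 0.05 × 0.95 / 0.05² = 73.0, and with the population of 700, n = 73.0 / (1 + 72.0/700) = 66.2. That formula has no term for attrition and no link to the primary averages.

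**Inputs.** Five-day minimum (section 4.0), mean stay of 12 days and target of 66 (section 5.0). Assumptions: remaining stay is exponential with mean m; shorter means of 9 and 6 days are tried because time may pass before enrolment and these patients are near death. A mean of 3 days is shown only as an extreme, since three days is an entry minimum and not a cohort average.

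**Step 1, early exit and observed time.** P(leave before five days) = 1 − exp(−5/m). Mean time observed in the five-day window = m × (1 − exp(−5/m)). At a constant rate of increases, the share of the five-day count captured is that time divided by 5.

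| Mean m (days) | Leave early | Of 66 | Days observed | Share of count |
|---|---|---|---|---|
| 12 | 34.1% | 22.5 | 4.09 | 82% |
| 9 | 42.6% | 28.1 | 3.84 | 77% |
| 6 | 56.5% | 37.3 | 3.39 | 68% |
| 3 (extreme) | 81.1% | 53.5 | 2.43 | 49% |

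**Step 2, shift in a day-5 average over those present.** Let leavers' pain differ from stayers' by d points, with no drug effect. The average over all patients is the stayers' average plus P(leave) × d, so the stayers' average misses it by P(leave) × d.

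- d = +1 to +2: too low by 0.34 to 0.68 points (m = 12) or 0.57 to 1.13 points (m = 6).
- d = 0: no shift.
- d = −1: too high by 0.34 (m = 12) or 0.57 (m = 6).

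A simulation with no drug effect (pain mean 5, SD 2, both assumed) agrees in pattern. If the correlation of survival with pain is −0.3 to −0.5, the survivor average falls by 0.33 to 0.55 points (m = 12) or 0.55 to 0.90 (m = 6). At correlation 0 it does not move. At +0.3 it rises by 0.34 or 0.54.

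**Step 3, does within-patient change cure it?** A constant difference in level between leavers and stayers cancels. A difference in course does not. With pain rising on average 0.2 points a day (SD between patients 0.3, both assumed), the true five-day change is 1.0. At m = 12, completers alone show 0.59 if survival and slope correlate at −0.5, 1.0 at zero correlation and 1.25 at +0.3. Change from baseline is therefore better than averages over those present, but it still needs a rule for leavers.

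**The case against.** The strongest reply is that section 10.0 states no handling at all, only a commitment to report. An average could be formed per patient over the days observed, so that early leavers still contribute. The recorded baseline and the daily tracking of changes in section 4.0 allow a within-patient reading, under which a constant difference in pain level drops out. This is an exploratory pilot, and the only mean stay given is 12 days. Length of stay may include live discharges, so the exit figures are illustrative.

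Much of this stands. A reader might infer that the plan prescribes averaging over survivors. It does not; that is the likely default when no denominator is given. A reader might also infer that the results will be flattered because the sickest patients drop out. No passage links early death to pain or opioid use, and Step 2 shows that the shift can be zero or reversed. Nor does inability to self-report carry over to opioid dose, which does not depend on the patient's report; it affects pain and Edmonton scores.

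What does not stand is the suggestion that this is only missing detail. The within-patient reading is available but not adopted: section 4.0 specifies changes when it describes the secondary calculations and plain averages for the primary ones. A raw count of increases is cut short by early exit whichever patients leave. A mean of each patient's observed days would still cover stays of different lengths.

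**Conclusion.** The concern holds as a gap with consequences, and the SAP should close it. The named summaries, with missing data only noted, allow a change in who is measured to pass for a treatment effect. The exit rates of about 34%, 43% and 57% rest on exponential remaining stay with means of 12, 9 and 6 days; only the 12 comes from the documents.

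For pain and daily morphine equivalents the direction is unknown: favourable if leavers have more pain or higher doses, nil if exit is unrelated to them, reversed if leavers have less. For raw counts of increases the direction is known: low relative to a full five-day window, with about 82% captured at a 12-day mean and less at shorter stays, given a constant rate. The documents do not support a firmer statement that the pain and dose results are biased in the drug's favour.

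**What to change.** Amend section 10.0 as follows:

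- Analyse every patient who takes at least one capsule.
- For pain and morphine equivalents, use each patient's change from the recorded baseline in daily values (the daily mean for pain), for example with a repeated-measures model, in place of averages over those present. Such a model relies on missing-at-random and implicitly carries values past death, so it is not sufficient alone.
- Add a prespecified sensitivity analysis in which death, inability to self-report or stopping before day 5 counts as not improved, with improvement defined in advance.
- Report opioid increases per patient-day observed.
- Show the number contributing each day, and the last pain and morphine-equivalent values of those who left, by reason for leaving.

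The sponsor must also reconcile the three-day life-expectancy criterion in section 7.0 with the five-day minimum in section 4.0.

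The cost is SAP wording and a modest amount of extra analysis on data already to be collected. The not-improved analysis will look less favourable than averages over available patients.

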11.0 Informed Consent Process

See attached Informed Consent waiver.

All patients will be given, in addition to the written consent form, a simple verbal explanation of the study's goals and methods to ensure full consent. (Translated as applicable)

Privacy and confidentiality

Human subject's names will be kept on a password protected database, and will be linked only with a study identification number for this research. There are no patient identifiers. All data will be entered into a computer that is password protected. Data will be stored in a locked office of the investigators and usually maintained for a minimum of three years after the completion of the study.

